Women who are pregnant or lactating will be excluded to minimize the confounding effects of reproductive hormones on myocardial metabolism. Women of child-bearing age will be on effective contraception (e.g., stable dose oral contraceptive, IUD), because fibrates are contraindicated in pregnancy. Efforts will be made to study menstruating women at the same point in their cycle.

Subjects with evidence of renal damage (e.g., creatinine > 1.5 mg/dl) will also be excluded, as will individuals with systemic illness or significant anemia (hematocrit < 28), history of biliary or liver disease, or history of recreational drug use or moderate to severe alcohol use (equivalent of > 5 glasses wine/wk). Subjects will also be excluded if they have a history of allergic reaction to fenofibrate.

METHODS

The study coordinator will describe the study to prospective subjects and may meet with them to answer questions. Interested potential subjects will be given the consent form to consider. Those potential subjects who indicate a willingness to participate will be scheduled for a screening appointment in the Center for Applied Research Sciences (CARS) at which time the signed consent form will be obtained prior to interview or any testing. Potential subjects will be asked to fast for 12 hours overnight prior to this visit; this may require a

temporary change in their diabetic medication regimen, which will be directed by a physician. Subjects will otherwise be continued on their stable outpatient medical regimens, including lipid-lowering therapy. We will be able to monitor and treat abnormal glucose level, if necessary, in the CARS. During this screening (VISIT 1) the following evaluation will occur:

- a. A general medical history questionnaire will be filled out by the subject.
- b. Urine will be obtained for urine pregnancy test (for female subjects).
- c. An intravenous (IV) catheter will be placed in an arm vein and blood will be obtained to evaluate for evidence of end-organ damage related to diabetes or systemic illness and to assess glucose and lipid levels (18 ml or approximately 4 teaspoons for HbA1c, complete blood count (CBC), complete metabolic panel (CMP) and lipid panel).

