- d. Subjects will undergo electrocardiogram (ECG) stress echocardiography in the Cardiovascular Imaging and Clinical Research Core Laboratory or the Cardiac Diagnostic Laboratory (CDL) at Barnes Jewish Hospital to rule out occult coronary artery disease and cardiomyopathy. If the images obtained are not adequate, Definity or Optison contrast will be administered intravenously.

Potential subjects who have had recent blood tests (within 3 weeks of scheduled screening visit) or stress testing (within 12 months of scheduled screening visit) may not need to repeat all of the scheduled screening tests if recent test results are available. They will be asked if they give permission for study investigators to access their medical record for the purpose of obtaining these specific results.

Potential subjects who do not know their triglyceride level or their HbA1c but are otherwise eligible may be asked to come in to the CARS for a pre-screening blood draw to determine eligibility. They would be asked to fast for 12 hours overnight prior to this visit; this may require a temporary change in their diabetic medication regimen, which will be directed by a physician. If their blood tests indicate they are eligible, they would then be scheduled for their Visit 1. Thus, for some potential subjects, screening may be divided into two sessions.

Subjects who qualify for the study will then return on a second day following an overnight (12 hr) fast for study VISIT 2 to undergo metabolic phenotyping and to begin intervention. This visit will involve CARS, the Cardiovascular Imaging and Clinical Research Core Lab and CCIR and includes:

- a. Urine will be obtained for biochemical analysis of oxidative stress and for urine pregnancy test (female subjects).
- b. An IV catheter will be placed in an arm vein and blood (30 ml or approximately 2 tablespoons) will be obtained to determine lipid biomarkers, genetic markers, markers of oxidative stress and systemic inflammatory markers (hsCRP, TNFalpha, and IL-6).
- c. Body fat and fat-free mass will be determined by dual energy x-ray absorptiometry scan (DXA).
- d. Cardiac structure and function will be quantified by transthoracic echocardiography using two-dimensional (2D), Doppler, and tissue Doppler imaging. If the images obtained are not adequate, Definity or Optison contrast will be administered intravenously.
- e. Subjects will undergo ¹H-MRS imaging so that hepatic triglyceride can be quantified.

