- f. After this baseline testing is complete, subjects will be randomized (using randomization.com to create block randomization) in a blinded fashion to treatment with fenofibrate (160mg/d), a prescription medicine approved by the Food and Drug Administration for treatment of hypertriglyceridemia in adults, or identical-appearing placebo for 12 weeks.
- g. Subjects will be instructed by the study coordinator to continue their usual medications, diet and level of physical activity. They will be given a pedometer to wear daily in order to track their physical activity. Study subjects will be instructed to record blood glucose concentrations and distance walked daily in a study-supplied log. They will also note in this log any side effects, major illnesses or stresses, since TGs are acute phase reactants. Subjects will be asked to either send the log by fax or email to the study coordinator each week or to discuss the log by telephone with the coordinator each week, so that this information can be reviewed by the study investigators.

- h. Through the Lifestyle Intervention Core, subjects will complete a 24-hour dietary recall to provide insight into dietary exposures.

Subjects will return at 6 weeks following start of the intervention for study VISIT 3 for medical monitoring to ensure medical safety. If this visit cannot be scheduled 6 weeks into the intervention due to staffing/scheduling conflicts, it will take place at 5 weeks so that the medical monitoring can be accomplished in a timely fashion.

At this visit:

- a. An interim history will be obtained by the study coordinator and reviewed with the study investigator. Study coordinator will also perform pill counts to assess compliance.
- b. The log of blood glucose, distance walked, side effects and major illnesses/stress will be reviewed by the study coordinator and discussed with the study investigator.
- c. Women will provide a urine sample for a pregnancy test.
- d. Phlebotomy will be performed (6 ml or less than 2 teaspoons) to rule out untoward effects of study drug on kidney or liver function (CMP).
- e. A dietitian will again assist the subject with completing a 24-hour dietary recall.

Subjects will return 12 weeks following start of intervention for study VISIT 4 at CARS for the following:

- a. Urine will be obtained for biochemical analysis of oxidative stress.

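### Minor, low-cost safety improvement: no pregnancy test is scheduled at Visit 4 (week 12), so the last 6 to 7 weeks of dosing are not followed by one

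*Protocol*

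**What the plan says.** The Protocol's METHODS section lists the procedures visit by visit.

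- Visit 1 (screening), item b: "Urine will be obtained for urine pregnancy test (for female subjects").
- Visit 2 (baseline, before the first dose), item a: "Urine will be obtained for biochemical analysis of oxidative stress and for urine pregnancy test (female subjects").
- Visit 3, item c: "Women will provide a urine sample for a pregnancy test". The visit is due 6 weeks after treatment starts. If it cannot be scheduled then, "it will take place at 5 weeks so that the medical monitoring can be accomplished in a timely fashion".
- Visit 4 (12 weeks after treatment starts), item a: "Urine will be obtained for biochemical analysis of oxidative stress". The blood assays in item b include no pregnancy test, and items c to f are the dietary recall, the log review, the liver spectroscopy and the echocardiogram.

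INCLUSION/EXCLUSION CRITERIA excludes pregnant women and states that "Women of child-bearing age will be on effective contraception", the reason given being "because fibrates are contraindicated in pregnancy". No visit after Visit 4 is described.

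**The concern.** The protocol treats pregnancy on fenofibrate as something to be avoided and checks for it three times. It does not check when dosing ends, although women give urine at that visit anyway. A woman who conceives after Visit 3 and does not yet know it would finish the trial, with no later visit, without any scheduled test having had a chance to show the pregnancy.

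What is at stake is ascertainment. An exposed pregnancy might not be recorded, the woman might not be told at the time, and nobody would follow it up. The point concerns the safety schedule. It does not touch sample size, power or type I error.

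**Working it through.** The protocol gives no figure of its own to reproduce, so the check is a comparison of the visit lists, one subtraction, and a bound on how much a fourth test could find.

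**Visit lists side by side**

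| Visit | Timing | Urine collected | Pregnancy test listed |
|---|---|---|---|
| 1 | screening | yes | yes (item b) |
| 2 | baseline, before dosing | yes | yes (item a) |
| 3 | week 6, or week 5 | yes, from women | yes (item c) |
| 4 | week 12 | yes (item a) | no |

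Visit 4 item a matches the opening of Visit 2 item a but lacks the part about the pregnancy test.

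**Dosing time with no later scheduled test**

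Interval = week of Visit 4 minus week of Visit 3.

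- Standard timing: 12 − 6 = 6 weeks.
- Fallback timing: 12 − 5 = 7 weeks.

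**What a Visit 4 test would reach**

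Let L be the time from conception to a positive urine test. The documents give no value; I assume 1 to 3 weeks. A test at week 12 would be the first able to show conceptions between (week of Visit 3 − L) and (12 − L). That span is 6 or 7 weeks long whatever L is. Conceptions in the last L weeks of dosing would still be missed.

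**Why few cases should be expected**

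The inputs are the recruitment goal of 130 subjects and the goal of about 50% women, both from INCLUSION/EXCLUSION CRITERIA.

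- Women at the goal: 130 × 0.5 = 65, both arms together.
- Woman-years after Visit 3: 65 × 6/52 = 7.5, or 65 × 7/52 = 8.75.
- Annual rate at which one case would be expected: 1/8.75 = 0.114 to 1/7.5 = 0.133, that is, 11 to 13 per 100 woman-years.

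This rate would have to hold for pregnancies that are new, detectable and still unrecognised at week 12. It counts all 65 women, although the age range runs to 65 years and women of child-bearing age must use contraception. If only 30% to 50% are of child-bearing age (an assumption), the rate needed rises to between 0.114/0.5 = 0.23 and 0.133/0.3 = 0.44 per woman-year. I judge such rates implausible under required contraception, so fewer than one case should be expected, by a wide margin. A closer estimate would need contraceptive failure and recognition rates that the protocol does not give, so I offer none.

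**The case against.** The best defence is that the schedule has a logic. Each listed test comes before a decision or an exposure: Visit 1 before eligibility is settled, Visit 2 before the body-composition X-ray scan and the first dose, and Visit 3 before drug is continued. At Visit 4 no dosing decision remains, and the X-ray scan is not repeated. There are other safeguards too. Contraception is required, logs are sent or discussed weekly and reviewed at Visit 4, and "Efforts will be made to study menstruating women at the same point in their cycle". The consent pages are not in this copy and may tell women to report a pregnancy.

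Most of this stands, and it is why the point is minor. It does not close the gap. Contraception can fail. The log contents do not name pregnancy, and a log can show only what the woman has noticed. Visit 3 has the same log review and still includes a test, so the protocol does not treat the log as a substitute there.

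A reader might infer more than the documents support:

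- *That the protocol contradicts itself.* It does not. It nowhere promises a test at every visit or at the end of treatment.
- *That the trial has no way to learn of an exposed pregnancy.* Only the absence of a scheduled test at Visit 4 is established. Self-report remains possible.
- *That the omission leaves women exposed for longer.* Dosing ends at Visit 4, so a test there neither prevents nor shortens exposure.
- *That the week-12 echocardiographic comparison is at risk.* The protocol does exclude pregnancy as a confounder of myocardial metabolism, but with well below one case expected any effect on the comparison is negligible.
- *That possible echo contrast at Visit 4 makes a test necessary.* The protocol states no pregnancy-specific risk from contrast, so this adds nothing.

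**Conclusion.** The point holds as a small improvement to the safety schedule. The last 6 to 7 of 12 dosing weeks are followed by no scheduled pregnancy test, so an exposed and unrecognised pregnancy would not be detected by the schedule. That rests on the protocol's visit lists and timings alone and is certain.

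The benefit of changing it is small: an expected yield well below one pregnancy, no exposure prevented, and very recent conceptions still missed. The size of the yield is a judgement, based on the recruitment goals being met and contraception being used as required. The case for acting is that the cost is lower still, and that a missed case would be a pregnancy exposed to a contraindicated drug with no record and no follow-up.

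**What to change.** Replace the text of Visit 4 item a with that of Visit 2 item a, so that the one urine sample serves both purposes. Then add a sentence that names pregnancy, because DATA AND SAFETY MONITORING does not mention it. Suggested text:

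*A positive result will be recorded on the CARS Data and Safety Monitoring Forms, the subject will be told, and the coordinator will contact her for pregnancy follow-up; the remaining Visit 4 assessments proceed at the investigator's discretion.*

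The cost is one test strip per woman, at most about 65 at the enrollment goal, and two short text changes. No extra sample or visit is needed for the test itself. A positive result would also require contact after Visit 4. The protocol does not yet provide for this: its FOLLOW-UP section covers only the release of test results.

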1. Test whether pharmacological approaches to lower delivery of excess lipid to the heart in human subjects with T2DM improves cardiac function.
2. Determine whether specific lipid molecular species in plasma, quantified by highly sensitive mass spectrometry based lipidomic profiling, can serve as biomarkers for diabetic cardiomyopathy.

This study will provide novel insights into the relationship between lipid metabolic abnormalities in diabetes and cardiac function. This study may result in new diagnostic and therapeutic approaches to diabetic cardiomyopathy.

INCLUSION/EXCLUSION CRITERIA

Subjects will be recruited from clinics, practices, and laboratories within the Barnes-Jewish Hospital consortium, from the Volunteers for Health program and the Diabetes Research Connections recruitment program at Washington University School of Medicine, and through the use of local advertisements, posters, emails and flyers. Proposed dates of enrollment are from 4/1/12 through 2/28/18. One of the principal investigators or their proxy will address all questions of potential participants before written informed consent is obtained and prior to all studies. Consent procedures and forms will be approved by the Human Research

Protection Office (HRPO). Should a subject choose to withdraw from the study at any time, blood and tissue samples will be destroyed.

Because diabetes and diabetic cardiomyopathy commonly occurs in women, it is important that women are adequately represented among study participants. Our goal is to achieve ~50% enrollment of women in this study. Diabetes and diabetic cardiomyopathy commonly occurs in minorities. Thus, it is equally important that adequate numbers of subjects from these groups are represented among study participants. Our goal will be to recruit a total of 130 subjects of different ethnic and racial backgrounds in proportion to their representation in the greater St. Louis population.

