- b. Fasting (12 hr) phlebotomy (35 ml or less than 2.5 tablespoons of blood) to determine complete metabolic panel, lipid panel, lipid biomarkers, genetic markers, markers of oxidative stress and systemic inflammatory markers (hsCRP, TNFalpha, and IL-6). An IV catheter will be placed in an arm vein to obtain this blood.
- c. Subjects will complete a 24-hour dietary recall to provide insight into dietary exposures.
- d. Subject's log of blood sugars, distance walked, side effects and major illnesses/stress will be reviewed by study investigators.
- e. ¹H-MRS imaging of the liver will be repeated to assess the effects of intervention on systemic lipid exposure.
- f. Echocardiographic studies will be repeated to assess cardiac function. If the images obtained are not adequate, Definity or Optison contrast will be administered intravenously.

REMUNERATION

Subjects who qualify for the study, choose to enroll, and complete all aspects of this study will receive \$250 for their time and inconvenience, in the form of a check, approximately 6 weeks after completion of the study. If a subject qualifies for the study, chooses to enroll, but completes only Visit 1 (screening) and Visit 2 (metabolic phenotyping), the subject will receive \$25 in the form of a check.

RISKS OF THIS STUDY

Screening health questions:

Likely: None

Less Likely: None

Rare: Subjects may experience emotional discomfort when answering some questions during the screening interview with study personnel. Subjects do not need to answer questions that make them uncomfortable. However, if they refuse to answer the question regarding implanted metal objects, they will not be able to undergo the magnetic resonance imaging (¹H-MRS spectroscopy) and therefore will be excluded from the study.

Overnight fast:

Likely: None

Less Likely: Blood sugar may become too high or too low while fasting. Patients will be counseled ahead of time regarding dosing of anti-diabetic medications and blood sugars will be monitored in CARS and treated appropriately.

Rare: None

Phlebotomy:

Likely: None

Less Likely: Risks associated with sampling of blood include pain, bleeding, and bruising.

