Less Likely: Minor side effects include abdominal symptoms (abdominal pain, nausea, vomiting, diarrhea, constipation and flatulence), photosensitivity, myositis or myopathy, and headache. Subjects will be monitored for all of these symptoms and for elevation of liver function tests (alanine aminotransferase [ALT] and aspartate aminotransferase [AST]) as these can become elevated in some patients. Should any of these side effects develop, the subject will be withdrawn from the study.

Rare: There is a minimal risk of allergic reaction (1%). Medication interactions are rare but can occur with oral anticoagulants, HMG-CoA reductase inhibitors, bile acid sequestrants, and cyclosporin. Subjects on anticoagulants or cyclosporine will be excluded. Subjects on bile acid sequestrants and HMG-CoA reductase inhibitors will be monitored closely. Allergic reactions can be treated with diphenhydramine or epinephrine.

24-hour food recall:

Likely: None

Less Likely: None

Rare: Subjects may experience some emotional discomfort or frustration in recalling everything they ate and drank over 24 hours.

Blood glucose and event log:

Likely: None

Less Likely: None

Rare: Subjects may experience some emotional discomfort or frustration from recording their blood glucose levels, distance walked, major illnesses/stresses/side effects, and from reporting this information to the study coordinator each week.

PI: [name]

Placebo:

Likely: None

Less Likely: None

Rare: None

SUBJECT CONFIDENTIALITY

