The Data and Safety Monitoring Plan for this protocol will include adverse event reporting by the PIs on the CARS Data and Safety Monitoring Forms, with oversight and monitoring by the PIs and the Research Subject Advocate (RSA). The PIs and research coordinator will meet weekly to review any study issues, and a Data and Safety Monitoring Board consisting of [name] (Professor of Medicine and Medical Director of the Heart Failure Program at Washington University) and [name], MS (Biostatistician in the Division of Cardiology) will meet every six months with the study coordinator and Study Investigators to review study data, discuss any safety issues, ensure compliance with the protocol, and ensure the subjects' protection against risk.

Serious Adverse Events (SAEs) from this protocol will be reported to the CARS Advisory Committee via the CARS RSA, to the HRPO, and to the NIH. The study will be discontinued if there is clear evidence of harm or

harmful side effects of the procedures. In the event that a SAE occurs that increases the risks to participants, the study will be stopped, an investigation will be conducted, and a findings report generated to the NIH, HRPO, and CARS via the RSA before the study is resumed. Should there be SAEs or AEs that occur at a frequency greater than 5%, they will be added to the consent document, if not already addressed, and enrollment will be halted while a determination is made regarding the potential risks to participants. A report summary will be generated and sent to CARS and the RSA every 6 months. The summary report will include (but is not limited to) who monitored the study, SAEs, AEs, compliance, compliance with data collection, dropouts, and recruitment/enrollment.

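### A subject with a listed side effect leaves the study, not just study drug, so the week 12 echocardiogram is lost and Aim 1's randomised comparison is open to selection bias

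*Protocol*

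**What the plan says.** Aim 1 of the protocol (Objectives) is to "Test whether pharmacological approaches to lower delivery of excess lipid to the heart in human subjects with T2DM improves cardiac function". Subjects are randomised, blinded, to fenofibrate or a matching placebo for 12 weeks.

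The places that bear on who contributes an outcome are:

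- **Risks of this study, Fenofibrate.** After listing abdominal symptoms, photosensitivity, myositis or myopathy, headache and raised ALT/AST, all under Less Likely, the protocol states: "Should any of these side effects develop, the subject will be withdrawn from the study". It sets no severity or attribution condition. The Placebo entry lists no effects at any level.
- **Methods, Visit 2 (d), baseline.** "Cardiac structure and function will be quantified by transthoracic echocardiography".
- **Methods, Visit 3.** "Subjects will return at 6 weeks following start of the intervention for study VISIT 3 for medical monitoring to ensure medical safety". No echocardiogram is listed.
- **Methods, Visit 4 (f), week 12.** "Echocardiographic studies will be repeated to assess cardiac function".
- **Follow-up.** This section covers only the release of test results.
- **Remuneration.** A subject who enrols but "completes only Visit 1 (screening) and Visit 2 (metabolic phenotyping), the subject will receive" $25.
- **Inclusion/exclusion criteria.** "Should a subject choose to withdraw from the study at any time, blood and tissue samples will be destroyed".
- **Data and safety monitoring.** "Should there be SAEs or AEs that occur at a frequency greater than 5%, they will be added to the consent document", and enrolment is halted while the risk is assessed. Dropouts are reported every six months.

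**The concern.** The rule removes people from the study, and the protocol nowhere distinguishes that from taking them off study drug. Withdrawal is triggered by an event after randomisation that treatment can influence, and the only outcome assessment for Aim 1 comes at the end of treatment. Subjects who meet the rule before week 12 therefore drop out of the comparison that randomisation was meant to protect.

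The remaining subjects are balanced only if the rule removes similar people in similar numbers from both arms. Nothing in the protocol secures that. It attributes these effects to fenofibrate and lists none for placebo, although it gives no rates by arm. A baseline echocardiogram and a sound missing-data method can shrink the resulting bias but cannot fully repair it.

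**Working it through.** **Textual check.** The weekly log and the Visit 3 metabolic panel are designed to find side effects before week 12, so the rule can act before the Visit 4 echocardiogram. A transaminase rise first seen in the Visit 4 bloods need not cost that echocardiogram, so the loss concerns effects found earlier. No section provides a Visit 4 or an early-termination assessment for a withdrawn subject. The $25 payment and the destruction of samples fit this reading but do not prove it: the first covers non-completion for any reason, the second only subjects who choose to leave.

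**Inputs for the size.** The protocol gives only the recruitment goal of 130. Everything else is assumed:

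- 130 randomised 1:1, so 65 per arm;
- two-sided 5% test and an unadjusted completer comparison;
- withdrawal fractions pF (fenofibrate) and pP (placebo);
- a gap g of 0.5-0.8 SD in outcome between withdrawn subjects and completers, equal in both arms.

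**Formulas (SD units).**

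- Standard error: SE = √(1/n1 + 1/n0), with n1 = 65(1 − pF) and n0 = 65(1 − pP).
- Completer bias: g(pF − pP).
- Type I error: P(|Z + bias/SE| > 1.96).

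For 10% v 5%: n1 = 58.5 and n0 = 61.75, so SE = 0.1825. With g = 0.8 the bias is 0.8 × 0.05 = 0.04, bias/SE = 0.219, and the type I error is 5.55%.

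| Withdrawal, fenofibrate v placebo | Visit 4 echoes of 130 | SE | Bias, g = 0.5 to 0.8 | Type I error |
|---|---|---|---|---|
| 5% v 2% | 125.4 | 0.179 | 0.015-0.024 | 5.08-5.21% |
| 10% v 5% | 120.2 | 0.183 | 0.025-0.040 | 5.22-5.55% |
| 25% v 15% | 104.0 | 0.196 | 0.050-0.080 | 5.74-6.92% |

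The last row is a stress case. With 100 or 80 randomised, the bias in SD is unchanged and the top type I error becomes 6.47% or 6.18%. The bias is zero if g = 0 or, with the same gap in both arms, if pF = pP. Wider assumptions give more: 20% v 5% with g = 1.0 gives 0.15 SD and 12.5%. Nothing in the protocol supports those rates, and the conclusion does not use them.

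**If stoppers are asked to attend Visit 4.** If all attend, this bias is removed. If a random fraction r attends, the residual is g[h(pF) − h(pP)], with h(p) = p − pr/(1 − p + pr). For r = 0.5, h(0.10) = 0.0474 and h(0.05) = 0.0244. The residual is 0.0072-0.0116, 0.0115-0.0184 and 0.0191-0.0306 SD in the three scenarios.

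**Power.** At 65 per arm, 80% power corresponds to d = (1.960 + 0.842) × √(2/65) = 0.491 SD. The completer analysis uses d with the SE above. The as-randomised analysis uses √(2/65), with d(1 − pF) if stoppers lose all benefit and d(1 − pF/2) if they keep half.

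| Stopping on fenofibrate | Completers | As randomised, all benefit lost | As randomised, half kept |
|---|---|---|---|
| 5% | 78.6% | 75.9% | 78.0% |
| 10% | 76.8% | 71.3% | 75.9% |
| 25% | 70.6% | 55.6% | 68.8% |

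**The case against.** The strongest reply is that the effect is small. In the two scenarios short of the stress case the bias is 0.08 to 0.22 of a standard error, and every input is assumed. That stands as a limit on severity. It does not show that the loss is harmless, since the document gives no rates from which to rule out a larger one.

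Second, the trial is blinded and many triggers are non-specific, so placebo subjects will meet the rule too. This is fair and may narrow the imbalance. It does not guarantee equal loss, nor that the same kind of subject is lost from each arm. Likewise, the contrast between the fenofibrate and placebo risk entries is a risk listing, not a forecast of rates, so it supports only the statement that loss may differ.

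Third, the monitoring rule on events above 5% would probably trigger a review in the larger scenarios. It does not cap withdrawals, and neither that review nor the dropout report restores an echocardiogram.

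Fourth, Aim 1 can be read as a mechanistic question, for which subjects off drug are uninformative, and the choice of estimand may sit in an analysis plan not shown. That choice is indeed open. But the plan can choose only among data that the protocol collects.

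Finally, withdrawn may have been meant as off drug. Nothing in the text says so; if that is the intent, the protocol should say it.

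**Conclusion.** The concern holds and should be fixed. It is certain on the text that the protocol withdraws such subjects from the study and provides no later outcome assessment. The consequence for Aim 1 is conditional: there is bias only if loss, or the kind of subject lost, differs by arm and withdrawn subjects differ from completers in cardiac outcome. Under the stated assumptions it is modest, at most 0.08 SD with type I error just under 7% in the stress case, and its true size and direction cannot be derived from the document. Confidence is therefore medium. What justifies acting is that the lost data cannot be recovered later and that collecting them uses a visit already scheduled.

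**What to change.** Separate stopping study drug from leaving the study, and add a sentence to this effect:

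> A subject whose study drug is stopped for a side effect is asked to remain in the study and complete the planned Visit 4 assessments 12 weeks after the start of intervention, unless consent is withdrawn.

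This concerns outcome collection only. Which events lead to stopping drug is for the sponsor, and no change to that is proposed. The existing withdrawal statement must be reconciled with the new sentence so that the two do not conflict.

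The cost is one sentence in the protocol and the consent form, plus a line on payment, because full payment now depends on completing every aspect of the study. The statistical price is dilution of the as-randomised effect, to 95%, 90% or 75% of the on-drug effect in the worst case. No gain in power is claimed: the as-randomised analysis has lower power than the completer analysis in every scenario shown. The completer comparison remains available as a supplementary analysis, and which comparison leads can stay with the analysis plan.
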